## PRÉCIS

### **Background:**

- Human epidermal growth factor receptor 2 (HER2, also known as *c-erbB2* or *neu*) is a proto-oncogene that encodes a 185-kd transmembrane (TM) tyrosine kinase receptor that participates in receptor-receptor interactions that regulate cell growth, differentiation and proliferation. Its over-expression contributes to neoplastic transformation.
- HER2 is over-expressed in up to 25-30% of node-positive or node-negative primary breast cancers and is associated with clinically aggressive breast cancer, a high recurrence rate and reduced survival.
- Trastuzumab (Herceptin®) is a recombinant humanized mouse monoclonal antibody (MAb) that binds to the extracellular (EC) domain of the HER2 receptor. Its clinical efficacy is limited to patients with 3+ HER2 tumor expression documented by immunohistochemistry (IHC) or a HER2 amplified tumor by Vysis fluorescent *in situ* hybridization (FISH). IHC is a subjective measurement of HER2/*neu* protein while FISH is an objective measurement of amplification of the HER2 oncogene.
- Although the use of trastuzumab has been associated with improved clinical outcomes, a significant number of patients are unresponsive to therapy and most eventually experience clinical progression. At present, no vaccine is available that induces patients to make their own anti-HER2 antibodies.
- We propose to investigate the use of an adenoviral vector (Ad5f35) expressing *human* HER2ECTM (Ad5f35HER2ECTM- AdHER2) to transduce autologous dendritic cells for therapeutic vaccination in patients with HER2 expressing solid tumors.

### **Objectives:**

- To determine the safety and toxicity of autologous AdHER2 dendritic cell vaccination.
- Specifically, to determine if the fraction of patients with cancer therapeutics-related cardiac dysfunction (CTRCD), defined as a decrease in LVEF  $\geq 10$  percentage points, to a value LVEF to  $\geq 53\%$  (normal reference value for two-dimensional (2-D) echocardiography), is sufficiently low to warrant further development in subsequent trials.
- To determine the immunogenicity of autologous AdHER2 dendritic cell vaccination as measured by a 3-fold increase in anti-HER2/neu antibody concentration or a 4-fold increase in antibody dilution titers over baseline.

### **Eligibility:**

- Adults  $\geq 18$  of age
- Patients with 1+ to 3+ HER2/neu expression by IHC or a Vysis FISH result equivocal or positive.
- Part I: Naïve to trastuzumab (Herceptin™), pertuzumab (Perjeta™) and lapatinib (Tykerb™), ado-trastuzumab emtansine (Kadcyla™) or other HER2-directed therapies.
- Part II: Recurrent or progressive metastatic disease after standard of care HER2- targeted therapies with known clinical benefit; i.e. trastuzumab (Herceptin™), pertuzumab

(PerjetaTM), lapatinib (TykerbTM), ado-trastuzumab emtansine (TDM1) (KadcylaTM) or other HER2-directed therapies.

- Eligible malignancies:
  - Parts I and II: Malignant soft tissue and bone tumors and recurrent or progressive, metastatic solid tumors who have progressed on standard therapies (Note: Patients with metastatic cancer must have measurable disease per RECIST 1.1); or,
  - Part I only: Bladder cancer in the adjuvant setting (adjuvant bladder cancer patients):
    - Tumor stage T3a, T3b, T4a, T4b and any node positive disease regardless of tumor stage.
    - Status-post primary cystectomy with curative intent.
    - May or may not have received neoadjuvant cisplatin-based combination chemotherapy per NCCN guidelines.
    - May or may not have received adjuvant radiotherapy or chemotherapy based on pathologic risk per NCCN guidelines.
    - Greater than or equal to 6 weeks status post primary surgery with curative intent.
- Adequate hematologic, metabolic, hepatic, renal, and cardiac function

### ***Study Design:***

Open label, non-randomized, two-part, phase I study of 48 weeks duration for evaluation of primary endpoints with extended follow-up out to 30 months to monitor LVEF cardiac function.

**Part I** involves vaccine dose escalation in a population with no prior exposure to trastuzumab or other HER2-targeted therapies to determine if there is a significant, adverse safety signal regarding cardiac toxicity, in addition to preliminary assessment of the vaccine's immunogenicity and clinical activity in patients with metastatic solid tumors or high-risk bladder cancer in the adjuvant setting. Response will be evaluated by a Modified Immune-Related Response Criteria (modified irRC) based on Response Evaluation Criteria in Solid Tumors (RECIST 1.1).

**Part II** is identical to part I in the schedule of treatment and response evaluation, but is conducted in a population with prior exposure to trastuzumab and other HER2-targeted therapies.

## **1 INTRODUCTION**

### **1.1 STUDY OBJECTIVES**

#### **1.1.1 Primary Objective**

- To determine the safety and toxicity of autologous AdHER2/neu dendritic cell vaccination. Specifically, to:
  - Determine if the fraction of patients with cancer therapeutics-related cardiac dysfunction (CTRCD), (if it occurs) is sufficiently low to warrant further development in subsequent trials. CTRCD is defined as a decrease in LVEF  $\geq 10$  percentage points, to a value  $\geq 53\%$  (normal reference value for two-dimensional (2-D) echocardiography).
- To determine the immunogenicity of autologous AdHER2 dendritic cell vaccination as measured by a 3-fold increase in anti-HER2/neu antibody concentration (measured as mcg/mL) or a 4-fold increase in antibody dilution titers over baseline.

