### 3.1.1 Dose Limiting Toxicity

The following assessment guidelines for the management of dose limiting toxicity (DLT) are intended to ensure the safety of each patient while on the study. The descriptions and grading scales found in the revised NCI Common Terminology Criteria for Adverse Events (CTCAE) version 4.0 will be utilized for AE and DLT reporting. All appropriate treatment areas should have access to a copy of the CTCAE version 4.0. A copy of the CTCAE version 4.0 can be downloaded from the CTEP web site ([http://ctep.cancer.gov/protocolDevelopment/electronic\\_applications/ctc.htm#ctc\\_40](http://ctep.cancer.gov/protocolDevelopment/electronic_applications/ctc.htm#ctc_40)).

All adverse events will be classified as follows for determination of relatedness to AdHER2 vaccination:

- Unrelated
- Unlikely
- Possibly related
- Probably related
- Definitely related

For the purposes of this study, the definitions of dose limiting-toxicities include:

- CTCAE Grade 2 and greater allergic reactions
- CTCAE Grade 2 and greater autoimmune disorders
- CTRCD, defined as a decrease in the LVEF of > 10 percentage points, to a value in < 53%. Documentation of the above specified change in LVEF will require cardiac consultation for determination of clinical significance. Cardiac function deterioration clinically associated with apparent cardiotoxic agent use after off-therapy will be censored at the point of cardiotoxic agent use.
- CTCAE Grade 3 or greater organ toxicity (dermatologic, gastrointestinal, hepatic, pulmonary, renal/genitourinary, or neurologic) occurring within 30 days of vaccine administration that are at least possibly related to research in.

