## **11 STATISTICAL CONSIDERATIONS**

The primary objectives of this open label, single site, non-randomized, two-part, phase I study of AdHER2 DC vaccination are to determine if the fraction of patients with cardiac toxicity (if it occurs) is sufficiently low to warrant further exploration in subsequent trials and to determine an approximate estimate of the vaccine immunogenicity, as represented by the fraction of patients who develop at least a 3-fold increase in anti-HER2/neu antibody concentration (measured as mcg/mL) or a 4-fold increase in antibody dilution titers over baseline at the time points measured. An important secondary objective is to obtain a preliminary estimate of the proportion of patients who may experience tumor shrinkage or stabilization that is sufficient by modified immune response related criteria (modified irRC) to be considered stable disease, a partial response or better.

It has been reported that up to 7% of patients with HER2/neu expressing tumors treated with trastuzumab monotherapy for metastatic breast cancer developed clinically significant cardiac dysfunction including congestive heart failure. It would be considered acceptable if the therapeutic AdHER2 DC vaccine proposed for this study would produce no greater than that level of cardiac toxicity, but not acceptable if it were to be exceeded. In order to evaluate this using a limited number of patients, a two-part design, but incorporating an early stopping rule, will be implemented.

Statistical considerations pertaining to each part of the study are as follows:

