- *Two or more of 6 patients in a given dose develop evidence of cardiac toxicity, accrual will be stopped to that dose level. Accrual expansion of an additional 12 patients will occur in the next lower dose level to further evaluate for cardiac toxicity.*
- *Any death (unrelated to underlying primary disease) that occurs and is attributed as being possible, probably or definitely related to the investigational AdHER2 DC vaccine (FDA requirement).*

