## 11.2 PART II (MAXIMUM OF 30 EVALUABLE PATIENTS)

Since the risk for cardiac toxicity may differ in individuals who have previously received HER2-directed therapy, the FDA is requesting that repeat dose escalation of AdHER2 DC vaccination be conducted in Part II of the study *in a population with prior exposure to trastuzumab, pertuzumab, lapatinib, ado-trastuzumab emtansine (TDM1) and other HER2-directed therapies.* This population will include adults with recurrent or progressive, metastatic breast, gastric/gastroesophageal or other cancers with 1+ to 3+ HER2/neu expression by IHC or an equivocal or positive FISH result. Vaccine dose escalation will be repeated to again determine whether there is an adverse safety signal regarding cardiac toxicity, in addition to assessment of the vaccine's immunogenicity and clinical activity. Vaccine dose escalation, administration, re-staging assessment and early stopping rules that will be invoked that are identical to that conducted in Part I.

The goal is to accrue up to 30 evaluable patients in Part II of the study and treat them with the experimental AdHER2 vaccine.

Unless an early stopping rule is invoked in either Part I or Part II of the study, the number of patients who have experienced a clinically significant cardiac toxicity will be determined to estimate the frequency of cardiac toxicity. In addition, the dose level(s) at which toxicity is observed will also be examined.

*If in part I, dose escalations have taken place in the first three dose levels and 0 of 20 patients have experienced cardiac toxicity, Part II of the study in patients with metastatic breast cancer and prior exposure to HER2-directed therapies will proceed with vaccine dosing based on the safety confirmed in Part I and as outlined in Section 3.1.2.* A maximum accrual of 30 patients will be enrolled in Part II and patients will continue to enroll on that dose unless 3 patients have experienced cardiac toxicity.

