## **11.4 STUDY TERMINATION**

This study will be terminated for the following reasons:

- Completion of enrollment accrual and all scheduled monitoring studies for enrolled subjects.
- Development of clinically significant CTRCD toxicity (defined as a decrease in the LVEF of > 10 percentage points, to a value < 53%) in two or more of the first 10 patients enrolled in the study or four or more of the first 20 patients enrolled in the study.
- Failure to accrue study subjects in a timely manner.

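### The primary cardiac endpoint, CTRCD, is defined in two opposite ways, and Sections 11 to 11.3 do not say which event enters the primary fraction

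*Combined protocol and SAP*

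**What the plan says.** Four places define CTRCD.

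- **Précis, Objectives:** a fall of at least 10 percentage points, "to a value LVEF to $\geq 53\%$ (normal reference value for two-dimensional (2-D) echocardiography").
- **1.1.1 Primary Objective:** the same size of fall, "to a value $\geq 53\%$ (normal reference value for two-dimensional (2-D) echocardiography").
- **3.1.1 Dose Limiting Toxicity:** "defined as a decrease in the LVEF of > 10 percentage points, to a value in < 53"%. It adds: "Documentation of the above specified change in LVEF will require cardiac consultation for determination of clinical significance".
- **11.4 Study Termination:** clinically significant CTRCD, "defined as a decrease in the LVEF of > 10 percentage points, to a value < 53"%. This triggers termination at two or more of the first 10 patients or four or more of the first 20.

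The statistical text that governs the primary fraction does not use the term CTRCD. Section 11 sets the aim as to "determine if the fraction of patients with cardiac toxicity (if it occurs) is sufficiently low to warrant further exploration in subsequent trials". The accrual rule in 11.1 acts when "Two or more of 6 patients in a given dose develop evidence of cardiac toxicity". Section 11.2 says that "the number of patients who have experienced a clinically significant cardiac toxicity will be determined to estimate the frequency of cardiac toxicity". Section 11.3 promises 80% and 95% confidence intervals for the fraction with toxicity. None of Sections 11 to 11.3 gives an LVEF threshold or refers to any of the four definitions.

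Two other provisions matter. Eligibility (2.1.1.4) requires a baseline LVEF of at least 53%. Section 3.5.2.3 schedules echocardiograms at 11 post-baseline time points, from Week 4 to Week 124.

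**The concern.** The primary fraction is meant to inform whether development continues. An analyst who follows the objective literally counts falls that end at or above 53%. One who follows 3.1.1 or 11.4 counts falls that end below it. The same patients can then give different primary results.

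Three further points are open:

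- The size of the fall differs: at least 10 points in the objectives, more than 10 in the two rules.
- Section 3.1.1 sends the change for a judgement of clinical significance, and 11.2 and 11.4 use that qualifier. The objective and the accrual rule do not.
- None of the four definitions names the echocardiogram from which the fall is measured.

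**Working it through.** **1. The plan's own probabilities.** These are exact binomial tails. For three or more of 30, P = 1 − Σ(k = 0 to 2) C(30,k) p^k (1−p)^(30−k).

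- p = 0.03: 1 − (0.4010 + 0.3721 + 0.1669) = 0.060. Section 11.3 states 6%.
- p = 0.15: 1 − (0.0076 + 0.0404 + 0.1034) = 0.849. Section 11.3 states 85%.

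The expansion-cohort figures in 3.1.2 and 11.1 (two or more of 12) also reproduce: 4.9% at 3% and 55.7% at 15%. The arithmetic is sound for whatever event the rate p describes.

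**2. The two definitions side by side.** Assume the fall is measured from the entry echocardiogram. Let E be the entry LVEF and V a follow-up LVEF.

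- Wording A (Précis, 1.1.1): E − V ≥ 10 and V ≥ 53.
- Wording B (3.1.1, 11.4): E − V > 10 and V < 53, before any judgement of clinical significance.

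V cannot be both at least 53 and below 53, so no single echocardiogram meets both. Wording A also requires E ≥ 53 + 10 = 63. A patient who enters at 53% to 62% cannot be an event under the objective, however far LVEF falls.

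| Entry to follow-up | Fall | A | B |
|---|---|---|---|
| 65% to 54% | 11 | yes | no |
| 60% to 45% | 15 | no | yes |
| 62% to 52% | 10 | no | no |

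**3. Enumeration.** Take whole-number entry values 53 to 75 and follow-up values from 30 upward, with a fall of at least 10. The number of pairs is the sum of (E − 39) for E = 53 to 75, which is 14 + … + 36 = 575.

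- A only: the sum of (E − 62) for E = 63 to 75, which is 1 + … + 13 = 91.
- Neither: exact 10-point falls from entry values 53 to 62, which is 10.
- Both: 0.
- B only: 575 − 91 − 10 = 474.

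The ranges are assumed. The counts show how the definitions divide the possible falls; they are not probabilities.

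**4. Per patient.** With serial echocardiograms a patient can meet each wording at a different visit. In the sequence 68%, 56%, 48%, the 12-point fall to 56% meets A and the 20-point fall to 48% meets B. The objective does not always miss a patient who meets B.

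**5. Effect on the reported fraction.** The plan names no interval method, so exact Clopper-Pearson intervals are assumed. Suppose 3 of 30 patients fall by more than 10 points to below 53%, and nobody else has a qualifying fall.

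| Count | Arises when | Fraction | 80% CI | 95% CI |
|---|---|---|---|---|
| 3/30 | B, all three judged clinically significant | 10.0% | 3.7% to 20.9% | 2.1% to 26.5% |
| 0/30 | A, none has an intermediate echocardiogram at or above 53% with a fall of at least 10 | 0% | 0% to 7.4% | 0% to 11.6% |

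The upper limits for 0/30 are 1 − 0.10^(1/30) = 7.4% and 1 − 0.025^(1/30) = 11.6%. If all three patients have such an intermediate echocardiogram, A also gives 3/30.

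**The case against.** The strongest reply is that the symbol in the objectives is a slip and that nobody would report zero cases while three patients meet the protocol's own CTRCD toxicity rule. The objective itself calls 53% the normal reference value, entry requires at least that value, and 1.1.1 and 3.1.1 cite the same reference. The accrual rule also appears within 3.1.1, directly after the CTRCD definition. Sections 3.2 and 3.3 tie enrolment and cessation of immunization to toxicity as set out in 3.1.1, and 11.2 shares the clinical-significance qualifier with 11.4. On this reading the operational rules are workable, and 0/30 against 3/30 is a constructed extreme.

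Part of this stands. The operational text leans towards the 3.1.1 wording. The numerical contrast is a hypothetical bound, because the documents give no event rate under either definition, and 11.3 labels its own three-of-30 comparison as illustrative, not as a decision rule. The reference-echocardiogram point is minor, since baseline LVEF is used as the comparator elsewhere.

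It does not remove the problem. The wording occurs twice, once in the primary objective itself. The accrual rule speaks only of evidence of cardiac toxicity, and no sentence links the primary fraction to 3.1.1. Changing the 53% symbol alone would still leave 10 points or more against more than 10 points, and would not settle whether a fall judged not clinically significant counts.

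**Conclusion.** The concern holds: the first primary safety endpoint is wrong as written. Current text gives one term two definitions that no single echocardiogram can meet together, and the sections governing the primary analysis choose neither. In the illustration, the objective gives anything from 0/30 to 3/30 where 3.1.1 and 11.4 give 3/30. Section 11.3 associates three or more of 30 with 15% toxicity (85% probability) rather than 3% (6%), so the choice of definition could change how the result is read. This rests on measuring the fall from the entry echocardiogram, on exact intervals, and on all three cases being judged clinically significant. The contradiction itself needs none of those assumptions. The sample size and the stated probabilities are not in question. It should be corrected before the primary analysis.

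**What to change.** Reconcile the Précis, 1.1.1, 3.1.1 and 11.4 to one CTRCD definition, with one inequality for the 53% limit, one for the 10-point fall, and a named reference echocardiogram. The sponsor should confirm the clinical threshold; this review does not propose one.

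Then state in 11.1 to 11.3 that this is the event counted in the primary fraction and its 80% and 95% intervals. State also whether the accrual and escalation counts use the same event, and whether a fall judged not clinically significant is included.

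The cost is a wording amendment to four definitions and a short addition to the statistical section. It requires no new data, visits or patients, and no recalculation.

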#### **1.1.2 Secondary Objectives**

- To determine the preliminary activity of autologous AdHER2 dendritic cell vaccination as measured by the fraction of subjects who have stable disease, a partial response or better by modified immune-related response criteria.
- To determine the impact of autologous AdHER2 dendritic cell vaccination on tumor growth rate and regression rate constants.
- To characterize vaccine-induced antibody profiles using HER2 peptide microarrays, examining reactivity to HER2 extracellular (EC), transmembrane (TM) and intracellular (IC) domains.
- To characterize and measure function-associated mRNAs in whole blood, circulating tumor cells, myeloid derived suppressor cells (MDSCs) and other potential biologic/immunologic correlates of clinical response throughout treatment.

## **1.2 BACKGROUND AND RATIONALE**

### **1.2.1 HER2 Directed Therapies**

Human epidermal growth factor receptor 2 (HER2, also known as *c-erbB2* or *neu*) is a proto-oncogene that encodes a 185-kd transmembrane (TM) tyrosine kinase receptor that participates in receptor-receptor interactions that regulate cell growth, differentiation and proliferation. Its over-expression- either HER2 oncogene amplification and/or over-expression of the HER2 protein, contributes to neoplastic transformation. HER2 is over-expressed in up to 25-30% of node-positive or node-negative primary breast cancers and is associated with clinically aggressive breast cancer, a high recurrence rate and reduced survival. Development of agents targeting HER2 has resulted in expansion of therapeutic options and improved clinical outcomes for patients with HER2 over-expressing tumors. Current FDA-approved treatment options include trastuzumab and lapatinib. A third agent, pertuzumab is under priority review by the FDA with a decision expected by June 8th, 2012 for a proposed indication in combination with trastuzumab and docetaxel chemotherapy in patients with HER2-positive metastatic or locally

recurrent, unresectable breast cancer, who have not received previous treatment or whose disease has relapsed after adjuvant therapy.

#### 1.2.1.1 Trastuzumab (Herceptin®)

Trastuzumab (Herceptin®) is a recombinant humanized mouse monoclonal antibody (MAb) that binds to the extracellular (EC) domain of the HER2 receptor and was approved by the FDA in September 1998. It is approved for the adjuvant treatment of early-stage breast cancer with nodal spread (or without nodal spread if the tumor is high risk) as well as for first and second-line/salvage therapy for metastatic breast cancer. In the adjuvant setting trastuzumab is used in several ways:

- As part of a treatment course including chemotherapy with doxorubicin, cyclophosphamide and either paclitaxel or docetaxel, known as “ACTH”.
- With chemotherapy drugs docetaxel and carboplatin in a regimen known as “TCH”.
- Alone after treatment with multiple other therapies, including anthracycline-based therapy.

Trastuzumab has two approved uses in metastatic breast cancer:

- As first line treatment in combination with paclitaxel.
- As a single agent in patients who have received one or more courses of chemotherapy for metastatic disease.

Therapy typically involves an initial trastuzumab dose of 4mg/kg IV followed by 2mg/kg IV administered weekly for 52 weeks, alone (salvage therapy) or in combination with paclitaxel for the first 12 weeks (adjuvant and first-line therapy). However, clinical efficacy is limited to patients with 3+ HER2 tumor expression documented by immunohistochemistry (IHC) or gene amplification by fluorescent *in situ* hybridization (FISH). IHC is a subjective measurement of HER2/neu protein while FISH is an objective measurement of amplification of the HER2 oncogene. Despite the high level efficacy in combination with chemotherapy, the overall response rate of women diagnosed with HER2-positive metastatic breast cancer and treated with trastuzumab as a single first-line agent is only 26% clearly indicating there is room for improvement in therapeutic options. In addition, a significant number of patients are unresponsive to trastuzumab and most eventually experience clinical progression while on therapy, presumably due to trastuzumab resistance, whose mechanism is poorly understood.

Trastuzumab is also approved for use in combination with cisplatin and either capecitabine or 5-fluorouracil in treatment naïve patients with HER2-positive metastatic stomach cancer or cancer of the gastroesophageal junction.

Despite the success of trastuzumab, no vaccine is currently available that induces patients to make their own anti-HER2 antibodies.

